## 1. SYNOPSIS

Study Title	Design, implementation and assessment of a comprehensive community neonatal health package utilising medical and social interventions	
Internal ref. no.	N/A	
Study Design	Cluster randomised control trial	
Study Participants	The population of Preah Vihear (PVH) province, Cambodia	
Planned Sample Size	
 
293 villages with 586 Village Health Support Group Workers (VHSG)
 
26,500 children born in Preah Vihear over the study period and their parents (5,300 deliveries a year)
 
306 health centre nurses and midwives from 28 health centres and 17 health posts in Preah Vihear
 
30 nurses, 27 midwives and 18 doctors from Preah Vihear Referral Hospital
 
	
Planned Study Period	5 years	
	Objectives	Outcome Measures
Primary	The design, implementation and assessment of a comprehensive community neonatal health package utilising medical and social interventions	A comprehensive community neonatal health package utilising medical and social interventions
Secondary	Reduction of perinatal mortality in PVH province, Cambodia	A one third reduction in perinatal mortality in PVH province, Cambodia
Tertiary	To describe the characteristics of neonates, born in PVH province, Cambodia over a five-year time period	A document that describes the characteristics of neonates, born in PVH province, Cambodia over a five-year time period
	To develop a tool to undertake a full review of neonatal services and capabilities in PVH province, Cambodia	A user-friendly tool to assess neonatal healthcare services A report detailing neonatal services and capabilities in PVH province, Cambodia
	Design a fully comprehensive neonatal healthcare training and implementation package adapted to local need	A locally appropriate neonatal healthcare training and implementation package
	Establish regular VHSG meetings to address areas of concern for the local community with respect to childbirth and the neonatal period	Frequency and attendance rate of participants at the programmes VHSG group meetings

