## 5. STUDY DESIGN

A cluster randomised study design will be used, with a cluster being defined as a HC administrative group, as defined by the PVH Provincial Health Department. This includes all HC, HP, villages, and villagers in that group.

Pilot: to begin in July 2018, consisting of 4 clusters.

Intervention arm: to begin October 2019, consisting of 10 clusters.

Control arm: all remaining clusters.

Completion: December 2022.

The SBLP will be introduced into the provincial referral hospital during 2018.

The SBLP will be introduced into the new referral hospital during 2022.

The choice of which health centres will be included at each time point will be made using purposive sampling to ensure a mix of health centre characteristics. Characteristics that will be taken into account are the distance from the health centre to the referral hospital and number of villages the HC serves.

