#### **Primary Outcome:**

1. Perinatal mortality rate will be described by hazard rate and 95% confidence interval (CI) separated by groups. Survival between groups will also be described using Kaplan-Meier plot. Log-rank test will be used for univariate comparison of survival. We will also describe median time to perinatal death with 95% CI in each group from Kaplan-Meier plot.

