#### **Sample size Calculation**

With perinatal mortality rate and a simple parallel cluster randomised trial design, the number of clusters are fixed to the intervention and control arm clusters and the time-frame is fixed to five years. The change in study design has been necessitated by logistical reasons and the post-study power calculations are not relevant. We will report limitations to the power in write-up.

The statistical analysis will remain broadly the same, with the main difference being that we will no longer adjust for the confounding effects of time. The primary analysis will exclude pilot cluster results, and will only be conducted on the intervention and control arm clusters.

Please see the study Statistical Analysis Plan for full details.

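### Purposively chosen arms are compared on mortality with an unadjusted log-rank test, and the protocol neither says how births before October 2019 are handled nor uses them as a cluster baseline

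*Protocol*

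**What the plan says.** Section 5 (Study Design) calls the trial cluster randomised, but the choice of health centres for each time point "will be made using purposive sampling to ensure a mix of health centre characteristics". The characteristics considered are distance to the referral hospital and number of villages served. The timetable is "Pilot: to begin in July 2018, consisting of 4 clusters" and "Intervention arm: to begin October 2019, consisting of 10 clusters". Control is every other cluster, and completion is December 2022. The same section brings the programme into the provincial referral hospital during 2018.

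Section 8.1 (Perinatal Mortality, Primary Outcome) lists hazard rates by group, Kaplan-Meier plots, median time to death and one between-arm test: "Log-rank test will be used for univariate comparison of survival". No covariate, baseline rate or cluster term is named there.

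Section 8.1 (Sample size Calculation) says that after the design change "we will no longer adjust for the confounding effects of time". It then says: "The primary analysis will exclude pilot cluster results, and will only be conducted on the intervention and control arm clusters". It fixes the time-frame at five years, gives no range of birth dates, and refers to the SAP for full details.

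The Synopsis plans for "26,500 children born in Preah Vihear over the study period and their parents (5,300 deliveries a year"). The Perinatal Mortality part of Section 3.2 has village workers record births and neonatal deaths in their villages, with no start date by arm.

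**The concern.** When arms are not formed by chance, nothing in the design makes their underlying mortality equal on average. An unadjusted comparison then estimates the programme effect plus whatever difference already existed between chosen and remaining clusters. With about 24 clusters, each cluster's own earlier mortality is an obvious covariate, and the protocol's five-year birth count suggests that such records may exist.

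The missing birth window adds a second ambiguity. Births before October 2019 may be left out, or they may be pooled into the comparison. The first leaves any baseline difference unaddressed. The second also mixes unexposed births into the intervention arm and shrinks the estimated effect. On neither reading do the earlier births serve as a baseline.

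**Working it through.** **Inputs from the protocol.** 28 health centres (Section 3.3); 4 pilot and 10 intervention clusters; October 2019 to December 2022, which is 39 months; 5,300 deliveries a year; target reduction one third (ratio 0.667).

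**Assumptions, not in the protocol.** One cluster per health centre, equal in size, so control has 28 − 4 − 10 = 14 clusters. Perinatal mortality p of 15–40 per 1,000. Between-cluster coefficient of variation k of 0.2–0.4. Correlation of true cluster rates over time of 0.8. Two-sided alpha 0.05.

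**1. The plan's own figure.** 5,300 × 5 = 26,500, which reproduces exactly. July 2018 to December 2022 is 4.5 years and would give 23,850. The planned total therefore spans more than the 39 months after October 2019.

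**2. Births either side of October 2019.** Births per cluster per year: 5,300/28 = 189.3.
- After, 39 months: 615 per cluster; × 24 = 14,764.
- Before, 15 months (from July 2018): 237 per cluster; × 24 = 5,679.
- Before, 21 months (five full years to December 2022): 331 per cluster; × 24 = 7,950.
- Share before: 15/54 = 28% or 21/60 = 35%.

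**3. Imbalance that could arise with no programme effect.** SD of the true log rate ratio = k√(1/10 + 1/14) = 0.083, 0.124 and 0.166 for k = 0.2, 0.3 and 0.4. Two SDs upward is a ratio of 1.18 to 1.39; two SDs downward is 0.85 to 0.72. This assumes chance selection. Purposive choice could do better or worse.

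**4. Effect on the log-rank test.** With D deaths and a baseline ratio b, z = |ln b| × √(D × 10/24 × 14/24), and P(significant) = Φ(z − 1.96) + Φ(−z − 1.96). At 20–40 per 1,000, D = 295–591.

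| Baseline ratio, no programme effect | P(significant) |
|---|---|
| 0.90 | 15%–24% |
| 0.85 | 28%–49% |
| 0.80 | 47%–76% |

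Clustering is ignored here, so that the baseline problem is seen alone.

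**5. If earlier births are pooled unmarked.** Pooled ratio = s + (1 − s) × 0.667, with s the share before October 2019. For s = 0.278 it is 0.759; for s = 0.35 it is 0.783. This assumes equal arms and steady mortality apart from the programme.

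**6. What baseline adjustment would buy.** With variances of cluster log rates v₀ = k² + 1/d₀ and v₁ = k² + 1/d₁ (d = expected deaths per cluster before and after), I took p = 15, 30 and 40 per 1,000, k = 0.2, 0.3 and 0.4, and 15 or 21 earlier months: 18 scenarios.
- Regression on the earlier rate: variance removed = 0.8² × (k²/v₀)(k²/v₁) = 2%–35%.
- Expected slope on the earlier rate = 0.8 k²/v₀ = 0.10–0.54, because d₀ is only about 4–13.
- Before-after contrast with fixed cluster effects: variance relative to unadjusted = (v₀ + v₁ − 1.6k²)/v₁ = 0.90–2.74, above 1 in 17 of 18 scenarios. At 30 per 1,000, k = 0.3 and 15 months it is 1.60.
- At 15 per 1,000 and 15 months, d₀ = 3.55. The chance that at least one of 24 clusters has no earlier deaths is 1 − (1 − e^−3.55)²⁴, about 50%, and that cluster's raw log rate is undefined.

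**The case against.** The SAP is not at hand, and covariate adjustment is commonly settled there. Dropping time adjustment is also ordinary when a stepped design becomes a parallel one with concurrent controls. Both points are fair, and the SAP may contain an adjusted model. What stands against them is that the protocol itself commits to a univariate test for arms it has chosen purposively. An SAP that adjusts would have to be reconciled with that text.

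Four stronger readings are tempting and not supported:
- A reader might infer that births before October 2019 are discarded. The protocol excludes only pilot clusters and sets no birth window, so they may equally be pooled in.
- A reader might infer that baseline records certainly exist in every cluster. This is only implied by the five-year count and the province-wide recording. The records arrive through monthly village-worker meetings, and Section 3.2 places the baby health meetings in intervention health centres.
- A reader might call the earlier period pre-programme. It overlaps the 2018 introduction at the referral hospital, and distance to that hospital is one of the selection characteristics, so exposure may differ by cluster.
- A reader might infer that the design change reduced a fuller model to a univariate one. The protocol says only that time adjustment goes and that the analysis otherwise stays broadly the same.

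It is also true that no actual imbalance is shown. Choosing for a mix of characteristics may have balanced the arms on those two characteristics, though it gives no assurance about mortality itself.

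**Conclusion.** The point holds in limited form. As written, the protocol compares purposively chosen arms with an unadjusted test, leaves the birth window open and gives earlier births no role as a baseline. The main risk is bias. A pre-existing ratio of 0.85 would yield a spuriously significant result in roughly 28%–49% of trials at 20–40 deaths per 1,000. Pooling earlier births would move a true 0.667 to about 0.76–0.78. These sizes rest on 24 equal clusters and assumed mortality, and the 2%–35% variance gain also on assumed between-cluster variation and correlation. They are illustrative.

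Precision is the lesser argument and depends on the model. The gain belongs to regression on the earlier rate. A before-after contrast with fixed cluster effects is not equivalent and usually costs precision on the same inputs. This is a change that should be made; it does not show that the comparison is already biased.

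**What to change.** In Section 8.1:
- State that the primary mortality comparison uses births from October 2019 onward in the intervention and control clusters.
- Replace the univariate log-rank test as the primary comparison with a cluster-aware model: a cluster-level regression, or a Poisson or binomial model with a cluster random effect and a small-sample correction.
- Adjust for distance to the referral hospital and number of villages. Where births before October 2019 were recorded in both arms, add each cluster's earlier perinatal mortality as a covariate. Use a count model or a shrunken rate, not a raw log rate, so that clusters with no earlier deaths can be kept.
- Report the before-after by arm contrast only as a sensitivity analysis, and note that the earlier period overlaps the 2018 introduction at the referral hospital.
- If earlier records are missing in either arm, adjust for the two selection characteristics alone.

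The cost is protocol and SAP wording plus two or three degrees of freedom out of about 22. No new data are needed if the earlier births were recorded as the five-year count implies. Adjustment will not remove a baseline difference fully: with an expected slope of about 0.1–0.5, much of a lasting imbalance would remain, and the report should say so.

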### **3. BACKGROUND AND RATIONALE**

Globally the proportion of childhood deaths that occur in the neonatal period is increasing [1]. Since 1990 there has been a 47% reduction in deaths in children less than five years of age [2]. However, this rate of reduction has not been seen in infants four weeks of age or younger (neonates). It is estimated that 2.9 million neonates die each year, with one million of these occurring on the first day of life [3]. Neonatal mortality now makes up 44% of all deaths in children younger than five years [3]. The reasons why the fall in neonatal mortality has not mirrored that seen in children mortality, is complex and one that is not well explored in the literature.

Cambodia has met most targets of the 4th and 5th Millennium Development Goals, reducing child mortality and improving maternal health by investing in health systems [4, 5]. However, the Sustainable Development Goals call for further improvements and Cambodia continues to fall behind its neighbouring countries in reducing neonatal mortality [6].

One proposed explanation is that interventions that have been successfully employed to reduce childhood death do not reach the community and it is in the community where most neonates die [7, 8]. Another pervasive perceived barrier to providing neonatal care, particularly in remote and rural areas, is the misconception that neonatal care is difficult and expensive [9].

During the neonatal period, perhaps more than at any other time, there are deep rooted health practices and beliefs. These differ in different communities but often share common themes. Hot bed use, food avoidance in the mother postpartum, discarding colostrum and application of various substances to the umbilical cord (such as cow dung, petrol and ash) are examples of widely held practices [10-12]. Many of these practices are potentially harmful to the neonate and need to be addressed in the communities where they occur by community engagement and education.

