### **Perinatal Mortality**

The expected outcome of the SBLP is a reduction in perinatal mortality (PMR). In order to assess the effectiveness of the SBLP an accurate measure of PMR is needed. Although births and deaths are required to be registered in Cambodia, often the births and deaths of young infants, particularly those born at home, are not registered. To accurately determine the perinatal mortality rate (PMR) in PVH province, government village health support groups (VHSG) will be asked to record details of all births and neonatal deaths in their villages. The data collected will include:

1. Village name
2. Estimated Date of Delivery
3. Date of delivery
4. Gender
5. Prematurity
6. Place of delivery
7. Birth weight
8. Alive at 28 days

The data will be brought to monthly VHSG meeting and entered in to a database by a member of the SBLT. Each VHSG will receive a \$2 phone credit card for each completed birth data collected. If a neonate dies, a verbal autopsy will be performed by one of the Saving Babies Lives team using the WHO Verbal autopsy tool [23].

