### **Economic Evaluation**

A detailed cost analysis will be carried out to estimate the added resources that are required for the SBLP as compared with standard care. These costs will be combined with estimates for the incremental cost of caring for children at AHC, and HCs if attendance is found to increase, and by modelling the subsequent survival benefits in terms of incremental disability adjusted life years averted. This will indicate whether the SBLP is as cost-effective as compared to the existing standard of care (control arm).

At the time of the newborn health questionnaire, the mother will be asked about any health seeking costs the family incurred for their infant in the first four weeks of life.

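### The promised Kaplan-Meier median time to perinatal death cannot be reached, and the birth data that the protocol names do not identify stillbirths or give the date or age at death

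*Protocol*

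**What the plan says.** Section 8.1 (Perinatal Mortality, Primary Outcome) plans a hazard rate with 95% CI by group, a Kaplan-Meier plot and a test: "Log-rank test will be used for univariate comparison of survival". It then adds: "We will also describe median time to perinatal death with 95% CI in each group from Kaplan-Meier plot".

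The data for this outcome are described in section 3.2 under Perinatal Mortality, whose stated purpose is an accurate perinatal mortality rate for the province. Village health support group (VHSG) workers "will be asked to record details of all births and neonatal deaths in their villages". Eight items are listed: village, estimated and actual date of delivery, gender, prematurity, place of delivery, birth weight, and "Alive at 28 days". The last is the only one about vital status. One further source on deaths is named: "If a neonate dies, a verbal autopsy will be performed by one of the Saving Babies Lives team".

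The secondary objective in section 4 is a one-third reduction in perinatal mortality. No baseline rate is given.

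**The concern.** There are two separate problems.

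First, the median of a group's Kaplan-Meier curve is the earliest time at which estimated survival falls to 0.5. For an outcome that affects a few per cent of births, the curve never comes near that level. The protocol promises a number, with a confidence interval, that cannot exist.

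Second, perinatal mortality includes stillbirths, and survival methods need a time for each event. The data items named in section 3.2 read as those of a neonatal outcome: births, neonatal deaths and status at four weeks. If the village record held only those items, the deaths counted would depend on whether a worker entered a stillborn infant as a birth. A stillbirth could not be told apart from a neonatal death. A death could not be placed in time, or inside any perinatal window shorter than 28 days. The analysis plan can define the outcome and choose the method, but it cannot supply an item that no form holds.

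**Working it through.** **The median**

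The protocol gives no median, event count or baseline rate to reproduce. Its one related figure agrees with itself: 5 years × 5,300 deliveries = 26,500 births (section 1).

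Inputs from the protocol:
- 5,300 deliveries a year and 28 health centres (section 3.3)
- 4 pilot clusters, 10 intervention clusters starting October 2019, all remaining clusters as control, completion December 2022 (section 5)
- pilot clusters excluded from the primary analysis (section 8.1, Sample size Calculation)

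Assumptions: one cluster per health centre, so 28 − 4 − 10 = 14 control clusters; equal births per cluster; mortality of 15 to 40 per 1,000 births.

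1. October 2019 to December 2022 is 39 months: 5,300 × 39/12 = 17,225 births.
2. Intervention: 17,225 × 10/28 ≈ 6,152. Control: 17,225 × 14/28 ≈ 8,612.
3. Deaths needed for survival of 0.5: 6,152/2 = 3,076 and 8,612/2 = 4,306.
4. Deaths expected at 15 to 40 per 1,000: 92 to 246 (intervention) and 129 to 344 (control).
5. With follow-up closed at 28 days and little censoring, the curve ends at about 1 − p, which is 0.985 at 15 per 1,000 and 0.960 at 40 per 1,000.
6. Lower 95% limit at 40 per 1,000, from 1 − p − 1.96 × √(p(1 − p)/n): 0.955 (n = 6,152) and 0.956 (n = 8,612). This ignores clustering. For the limit to touch 0.5 in the intervention arm, the half-width would have to grow from about 0.0049 to 0.46, roughly 94-fold.
7. Factor by which mortality would have to rise: 0.50/0.040 = 12.5 and 0.50/0.015 ≈ 33. This does not depend on the number of clusters.
8. Extreme check at 200 per 1,000: the curve ends at 0.80, with a lower limit of about 0.79 in both arms.

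**The data items**

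Setting what section 8.1 needs against what section 3.2 names:

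| Needed | Named in section 3.2 |
|---|---|
| Stillbirth or live birth | No item; the instruction covers births and neonatal deaths |
| Whether a live-born infant died | Yes, as status at 28 days |
| Date or age at death | No item; verbal autopsy follows a neonatal death but is not linked to the analysis |
| Date of delivery | Yes |

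To show the size of the stillbirth question, assume stillbirths of 10 to 15 and neonatal deaths of 15 to 25 per 1,000 births. Stillbirths are then between 10/(10 + 25) = 29% and 15/(15 + 15) = 50% of these deaths. The protocol gives neither rate.

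**The case against.** The strongest reply is that the median is one descriptive line. No test, sample size or conclusion depends on it, and software would simply return that it was not reached. That is fair as to weight: alone, this is a wording correction. It does not make the promised result obtainable. A median among deaths only could be computed, but it is not the median of the group's Kaplan-Meier curve, and it too needs times of death.

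On the data items, a reader might infer that stillbirth status and date of death are not collected. The protocol does not support that. The list is not worded as complete, and section 8.1 itself compares antenatal care visits between groups although they are not listed. Another instrument is mentioned but not shown: "At the time of the newborn health questionnaire, the mother will be asked about any health seeking costs the family incurred". Section 11.4 refers to a case report form, also not shown. Verbal autopsy may give age at death for neonatal deaths, and a count of all births does not exclude stillbirths. These objections stand and limit the claim to what the protocol states.

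A reader might also infer that most events would have no positive event time, because section 3 estimates that "2.9 million neonates die each year, with one million of these occurring on the first day of life". That goes too far. The figure is global, a first-day death need not fall on the calendar date of birth, and the stillbirth and neonatal rates needed for such a share are not in the protocol. Section 8.1 also fixes no time origin, and that choice can be left to the analysis plan.

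Finally, section 3.2 says of the records: "The data will be brought to monthly VHSG meeting and entered in to a database by a member of the SBLT". Because the Set-up paragraph places the baby health meetings in intervention health centres, a reader might infer that control villages have no way to hand in data. The opening of the same section has meetings at every health centre, and section 7.7 invites every VHSG worker, so that inference depends on choosing one of two readings.

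**Conclusion.** The point holds in two parts, with different confidence.

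The Kaplan-Meier median and its confidence interval cannot be reported in either arm. Confidence is high. The arm sizes rest on the assumed 28 equal clusters and the death counts on the assumed mortality range, but the conclusion needs neither, only mortality well below 500 per 1,000.

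The data that the protocol states do not support the perinatal survival analysis that it states, because nothing named identifies a stillbirth or gives the date or age at death. Confidence is moderate, since forms not shown may hold these items. Perinatal mortality is the outcome by which the programme's effect is to be judged, so which deaths are counted should be clear from the protocol. This should be fixed. No difference in recording between arms is claimed.

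**What to change.** 1. In section 8.1, delete the Kaplan-Meier median. Report cumulative mortality by arm at a fixed day, for example day 28, with a 95% CI that allows for clustering. Deleting the median costs nothing.
2. In section 3.2, reword the instruction to VHSG workers so that it covers live births, stillbirths and neonatal deaths.
3. Add two items to the village record: live birth or stillbirth, and date or age at death. If another form already holds them, name that form and say that it feeds the mortality analysis.
4. State that perinatal mortality is computed over all births, and report neonatal mortality separately.

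If the items already exist, the cost is a few sentences. If they do not, it is two form fields and possibly back-completion of stillbirth status and date of death in existing records.
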